6.10 Blinding

The subject, the investigator and site staff will be aware of the endometrial washing condition; however, the embryology lab will be blinded to the randomisation procedure and will not know the endometrial washing condition when preparing and/or evaluating embryos.

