7.1.3 Oocyte Retrieval Visit (Day 2 Post Randomization)

Subjects will return to the site approximately 34-36 hours after HCG triggering for oocyte retrieval and, when applicable based on randomisation, endometrial washing with Foriella for the Day 2 Post Randomisation (PR) visit. The following assessments and procedures will occur at the Oocyte Retrieval Visit (Day 2 PR):

- Oocyte retrieval (based on standard of care practices)
- Subjects randomised to Foriella will undergo endometrial washing per the Foriella IFU
- Provide luteal support/endometrial preparation (with 100 mg of intramuscular progesterone)
- Record adverse events, device incidents and concomitant medications
- Embryology lab will perform ICSI on oocytes retrieved
- Approximately 24 hours after ICSI, the embryology lab will perform daily embryo culture assessments to determine the embryo vitality and fertilization rate.
- The Embryology lab with the Doctor will determine how many embryos will be transferred and at which stage (e.g., either Day 5 PR or Day 7 PR), based on standard laboratory and clinical parameters. Definition of Embryo Transfer Visit should occur at this time point

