7.1.4 Embryo Transfer Visit (Day 5 or Day 7 Post Randomization)

Subjects will return to the site 3 to 5 days after oocyte retrieval for embryo transfer. If the embryologist determines the embryos should be transferred at the cleavage stage, embryo transfer will occur on Day 5 Post Randomization. If the embryologist determines the embryos should be transferred at the blastocyst stage, embryo transfer will occur on Day 7 Post Randomization.

| | |
|------------------------|---|
| Substance Code | Clinical Performance and Safety Investigation of ENDO metrial Washing ME dicinal DE vice Forielle |
| Protocol Number | MS 700623_0009 |

The following procedures will occur at the Embryo Transfer Visit:

- Embryo transfer (maximum of 2 embryos will be transferred); if no embryos are available for transfer, the subject will exit the study and study exit procedures, as applicable, will be performed
- Provide luteal support/endometrial preparation (600 mg vaginal progesterone to be used daily from the day after Oocyte Pick Up day)
- Calculate the fertilization rate (number of zygotes divided by the number of mature (MII) oocytes inseminated)
- Record adverse events, device incidents and concomitant medications
- Schedule the Post Embryo Transfer Visit 1 (Day 14 Post Embryo Transfer)

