8.2 Randomisation

Eligible subjects will be randomised to receive either the intervention (Forielle endometrial washing) or no endometrial washing following oocyte retrieval on Study Day 0, the HCG Triggering day, in a 1:1 ratio.

At the HCG triggering day, on study day 0 all eligible women subjects will be randomised in ratio of 1:1 to one of two parallel treatment groups:

- Forielle
- Control (No endometrial washing)

Women subjects will be stratified with respect two factors:

- Age (age <32; 32 ≤ age <38; 38 ≤ age ≤ 41)
- n° of follicles (>16mm) (5 ≤ n° follicles ≤ 9; 10 ≤ n° follicles ≤ 14)

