8.5 Description of Statistical Analyses

8.5.1 General Considerations

The study data will be reported using summary tables, figures, and data listings. Continuous variables will be summarized using mean, standard deviation (SD), coefficient of variation (CV%, as appropriate), median, minimum, maximum, and, as appropriate, geometric mean.

Descriptive statistics will be presented for key outcome measures. Categorical data will be summarized with the number of non-missing values and the numbers of values equal to each of the possible values. Percentages of subjects with each of the possible values will be calculated from the number of subjects in the corresponding analysis population, unless stated otherwise.

Unless otherwise specified, all formal statistical tests will be two-sided at the 5% significance level. Point estimates of treatment differences will be accompanied with two-sided 95% confidence intervals (CIs) where applicable. P-value will be used to draw statistical significant conclusions only for primary endpoint and for secondary endpoints all statistical estimates will be used for descriptive comparison.

In the case of normality assumption violations, appropriate non-parametric methods will be used for analysis.

All data will be presented in by-subject listings.

The statistical analysis will be performed using SAS[®] Version 9.2 or higher.

Substance Code Clinical Performance and Safety Investigation of ENDOmetrial Washing
MEdical DEvice Forielle
Protocol Number MS 700623_0009

All details regarding the statistical analysis and the preparation of tables, listings and figures will be described in a separate Statistical Analysis Plan (SAP) document developed by separately for interim and final analysis.

Study final analysis will be performed by PPD and Interim analysis will be performed by a PPD independent statistician from a different geographical region. A firewall will be implemented to ensure interim results will not be accessible to any PPD staff except to the independent statistician who will perform interim analysis.

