8.5.2 Analysis of Primary Endpoints

The primary endpoint subject implantation rate is defined as number of intrauterine gestational sacs divided by the number of embryos transferred, as assessed at PET Days 21 to 28.

Mean subject implantation rate as assessed at PET Days 21-28 in subjects treated with Forielle endometrial washing procedure will be compared to the mean subject implantation rate in subjects who receive no endometrial washing (control group) following COS.

For the primary endpoint analysis addition to summary statistics, differences in mean subject implantation rate between study procedure and control procedure will be investigated and compared using Gamma/log normal regression model. The analysis model will include treatment procedure as the fixed effect and Embryo Transfer Day (Day 5 PR or Day 7 PR), age, number of follicles at baseline and number of embryos transferred per subject as covariates.

To evaluate the treatment comparison, estimated mean differences will be presented together with two-sided 95% confidence intervals and p-values. Appropriate distribution will be decided based on good ness of fit (residual sum of squares) value.

This primary endpoint analysis will be tested by planned group sequential design with O'Brien-Fleming type spending function. The study for clinical performance will be stopped at significance level of 0.003 in first (50% of subjects) interim analysis and at significance level 0.049 in final analysis.

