8.5.3 Analysis of Secondary Endpoints

For the secondary endpoints, subject pregnancy result (positive/negative) and subject with confirmed pregnancy (yes/no), the pregnancy rate at PET Day 14 and ongoing pregnancy rate at PET Days 70-84 will be estimated and compared using logistic regression model including Embryo Transfer Day (Day 5 PR or Day 7 PR), age and number of follicles at baseline as covariates. Estimates of odds ratio, confidence intervals and relevant p-values will be presented for each endpoint.

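### The primary model adjusts for transfer day and number of embryos transferred, both set after randomisation with an arm-aware doctor's input; if the arm shifts them, the adjusted effect is biased

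*Combined protocol and SAP*

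**What the plan says.** The primary endpoint is gestational sacs divided by embryos transferred, per woman (section 8.3.1). For its analysis, section 8.5.2 says: "The analysis model will include treatment procedure as the fixed effect and Embryo Transfer Day (Day 5 PR or Day 7 PR), age"; the list continues with "number of follicles at baseline and number of embryos transferred per subject as covariates". The synopsis repeats this. Section 8.5.3 carries transfer day into the secondary endpoints, which are "compared using logistic regression model including Embryo Transfer Day (Day 5 PR or Day 7 PR), age and number of follicles at baseline". Only the primary endpoint is confirmatory: "P-value will be used to draw statistical significant conclusions only for primary endpoint" (section 8.5.1).

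On timing, women are randomised on Day 0 and washed at oocyte retrieval on Day 2; transfer is on Day 5 or Day 7.

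On who decides, section 7.1.3 says: "The Embryology lab with the Doctor will determine how many embryos will be transferred and at which stage". Section 7.1.4 words the stage choice differently: "If the embryologist determines the embryos should be transferred at the cleavage stage". On blinding, section 6.10 says: "The subject, the investigator and site staff will be aware of the endometrial washing condition; however, the embryology lab will be blinded".

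Section 8.2 states: "Women subjects will be stratified with respect two factors". These are age and number of follicles above 16 mm. Neither transfer day nor embryo number is among them.

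**The concern.** Randomisation balances what exists at Day 0. It does not protect a comparison made within levels of something fixed afterwards that may respond to the arm. Suppose the doctor, knowing a woman was washed, leans more often towards blastocyst transfer. The washed women at blastocyst stage then include some whose embryos would have gone at cleavage stage in the control arm. Within each stage the arms differ in embryo quality, and the model reads that as a treatment effect. The same holds for one embryo versus two.

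The two sections on who decides stage do not match, so the documents do not settle how far an arm-aware person influences it. Section 7.1.4 does not say who decides the number.

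At stake is the only confirmatory test in the trial. In the secondary models the same point is lesser, because those results are descriptive.

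**Working it through.** **Design figures (section 8.1).** Inputs: 0.25 versus 0.31, two-sided alpha 0.05, 80% power, two looks, O'Brien-Fleming spending. With pooled variance and continuity correction, the two-look calculation gives boundaries 2.963 and 1.969, and 916 per arm at power 0.800. With 15% dropout, 916/(1 − 0.15) = 1,078 per arm, or 2,156. The plan's figures reproduce. They rest on an unadjusted comparison of proportions, so removing covariates does not change them.

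**Illustrative model, no device effect.** The documents give none of the following inputs, so they are assumptions:
- Embryo quality Q is standard normal and raises implantation by 0.6 log-odds per SD; the mean rate is 0.25.
- The decision depends on Q with correlation ρ of 0.5 or 1 (at 1, quality alone decides).
- Control share: 50% blastocyst, or 30% single-embryo transfer. The wash-arm share varies.
- 916 per arm, 4,000 simulated trials per scenario, linear regression of the woman's rate with robust standard errors, tested at |z| > 1.969. This stands in for the planned gamma/log-normal model, so it shows the mechanism and not that model's exact error rate.

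**Transfer day, adjusted, two embryos each: bias in points (false rejection)**

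| Wash blastocyst share | ρ = 0.5 | ρ = 1 |
|---|---|---|
| 40% | +0.88 (7.9%) | +1.74 (22.2%) |
| 50% (no shift) | −0.03 (5.1%) | 0.00 (5.1%) |
| 60% | −0.85 (8.7%) | −1.67 (21.1%) |
| 70% | −1.70 (20.6%) | −3.33 (62.8%) |

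*Hand check of the 60% row.* At ρ = 1, mean Q in the blastocyst group is 0.399/0.5 = 0.798 in controls and 0.386/0.6 = 0.644 in the wash arm, a difference of −0.154. In the cleavage group the means are −0.798 and −0.386/0.4 = −0.966, a difference of −0.168. The average is about −0.161 SD. Multiplying by the slope 0.6 × 0.25 × 0.75 = 0.1125 gives −1.8 points at ρ = 1 and half that, −0.9, at ρ = 0.5. This is close to the simulated values.

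*Rejection check.* With two embryos and independence within a woman, SE = √(2 × 0.25 × 0.75/2/916) = 0.0143. A bias of 0.0085 is 0.594 SE, so rejection is Φ(−1.969 + 0.594) + Φ(−1.969 − 0.594) = 0.085 + 0.005 = 9.0%. A bias of 0.0167 is 1.167 SE and gives 21.2%. Both agree with the table.

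**Number transferred (one or two), adjusted, better embryos going to single transfer**

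| Wash single share | ρ = 0.5 | ρ = 1 |
|---|---|---|
| 20% | +0.96 (8.5%) | +1.97 (23.0%) |
| 30% (no shift) | −0.01 (5.5%) | +0.02 (5.0%) |
| 40% | −0.92 (7.7%) | −1.80 (18.1%) |

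If poorer embryos go to single transfer, the signs reverse: −0.81 to −1.62 at 20%, and +0.82 to +1.65 at 40%.

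**Without the covariate.** Bias is 0.0 points and rejection 4.1% to 5.7% in all these settings, provided stage has no effect of its own. With a stage effect of 0.5 log-odds, the unadjusted difference is +0.78 to +0.86 points (7.9% to 8.2%) at a 60% share and +1.59 to +1.68 (18.5% to 19.5%) at 70%.

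**Both decisions shifting together.** A separate large-sample run assumed quality at 0.5 to 1.0 log-odds per SD, a stage effect of 0.4 log-odds, and more blastocyst and more single transfers in the wash arm. Adjusted bias was −0.007 to −0.011 for 5-point shifts and −0.012 to −0.023 for 10-point shifts. The latter is 0.012/0.06 = 20% to 0.023/0.06 = 38% of the design difference. The unadjusted difference was 0.003 to 0.004 and about 0.007.

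**The case against.** The strongest reply is that nothing in the documents shows these choices will differ by arm. The wash acts on the uterus while the embryos are in culture, so the route is behavioural only. It is narrowed by a blinded laboratory, by a decision said to rest on usual laboratory and clinical criteria, and by section 7.1.4 naming the embryologist. This stands: it is a risk, not a demonstrated bias. It does not remove the doctor's role in section 7.1.3. The two sections could be read as one joint decision, which makes them ambiguous rather than flatly opposed; they still need one wording.

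Second, the illustration starts high. With ρ of 0.2 to 0.3 and a 5-point shift in stage, bias is −0.2 to −0.3 points and rejection 5.0% to 5.3%; at 10 points it is −0.4 to −0.5 points and 5.7% to 6.3%. That is fair, and such shifts would be harmless in practice. The plan offers no assurance that shifts will be that small.

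Third, dropping the covariates is not uniformly better. At a 70% share and ρ = 0.5, adjusted bias is −1.70 points, while with a 0.5 log-odds stage effect the unadjusted difference is +1.68. Section 5.2 presents implantation rate as a measure of endometrial receptivity, so one could argue for holding stage fixed. This also stands in part: the choice depends on the estimand. But the unadjusted figure is a real consequence of assignment, whereas the adjusted one mixes in a selection artefact that cannot be measured from the data.

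Finally, sections 8.4 and 8.5.1 leave detail to separate SAPs not seen here, so a baseline-only analysis may exist there. The primary model is nevertheless fixed in the protocol as written.

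**Conclusion.** The concern holds, and the plan should be changed on this point. Both variables are in the only confirmatory model, both are set after randomisation, an arm-aware doctor has a say in them, and the documents give no justification and no model limited to baseline covariates. The bias is conditional: zero if the arm does not influence the choices, and otherwise of either sign. Under the stated assumptions a 10-point shift in one choice gives about 0.8 to 2.0 points and 8% to 23% false rejection, against a design difference of 6 points. Weak links with embryo quality or smaller shifts bring this close to nothing. The wording facts are certain; the size is illustrative and comes from a linear model.

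**What to change.** - In section 8.5.2 and the synopsis, replace the covariate list with the randomisation strata: age (<32; 32 to <38; 38 to 41) and Day 0 follicles above 16 mm (5–9; 10–14). Keeping age and follicle number as continuous baseline terms would serve the same end.
- In section 8.5.3, drop transfer day from the descriptive secondary models in the same way.
- Keep the current models as labelled sensitivity analyses.
- Tabulate transfer day and number of embryos transferred by arm, so that a shift can be seen.
- Reconcile sections 7.1.3 and 7.1.4 on who decides the stage.

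The result then estimates the total effect of assignment among women who have a transfer. It does not remove an effect that runs through a shifted stage or through embryo number as the endpoint's denominator, and it gives no value to women without a transfer. The cost is protocol and SAP wording, with possibly a small loss of precision from dropping two prognostic covariates. The sample size of 2,156 is unchanged.

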As appropriate, variables will be summarized descriptively (frequency and percentage will be summarized for categorical variables; mean, standard deviation [SD], median, and maximum will be presented for continuous variables) by study visit and by treatment group. All study data will be listed by subject. A detailed Statistical Analysis Plan (SAP) including dictionaries used for coding and software used will be prepared separately for interim and final analysis. Study final analysis will be performed by PPD and Interim analysis will be performed by a PPD independent statistician from a different geographical region. A firewall will be implemented to ensure interim results will not be accessible to any PPD staff except to the independent statistician who will perform interim analysis.

Forielle Clinical Performance

The primary endpoint, subject implantation rate, is defined as number of intrauterine gestational sacs divided by the number of embryos transferred, as assessed at PET Days 21 to 28. Mean subject implantation rate, as assessed at PET Days 21 to 28 in subjects treated with Forielle endometrial washing procedure, will be compared to the mean subject implantation rate in subjects who receive no endometrial washing (control group) following COS.

For the primary endpoint analysis addition to summary statistics, differences in mean subject implantation rate between study procedure and control procedure will be investigated and compared using Gamma/log normal regression model. The analysis model will include treatment procedure as the fixed effect and Embryo Transfer Day (Day 5 PR or Day 7 PR), age, number of follicles at baseline and number of embryos transferred per subject as covariates.

To evaluate the treatment comparison, estimated mean differences will be presented together with two-sided 95% confidence intervals and p-values. Appropriate distribution will be decided based on good ness of fit (residual sum of squares) value. This primary clinical performance endpoint analysis will be tested by planned group sequential design with O'Brien-Fleming type spending function. The study for clinical performance will be stopped at significance level of 0.003 in first (50% of subjects) interim analysis and at significance level 0.049 in final analysis.

Safety

Device incidents will be summarized using frequency and percentages for two treatment groups.

Table 1-1 Schedule of Assessments

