8.1 Sample Size

The main aim of the study is the evaluation of the clinical performance of Forielle in restoring favourable condition of endometrial milieu, after Controlled Ovarian Stimulation. For this purpose, clinical performance will be measured by assessing the difference in implantation rate in the treated arm compared to the control (standard clinical practice). Generally, the average implantation rate of ART is considered of about 25% (Nastri et al. 2013). Several works in the literature suggested the key role of endometrial receptivity on the ART outcomes (Evans et al. 2012). An improvement of about 6% in implantation rate from the usual ART outcome is clinically relevant difference. Thus, for the calculation of sample size, a clinically important difference of 6% was assumed and an interim clinical performance analysis assuming that 2 sequential tests are made using the O'Brien-Fleming spending function to determine the test boundaries. Sample sizes of 916 each arm achieve 80% power to detect a difference of 0,06 between the group proportions of 0,25 and 0,31 at a significance level (alpha) of 0,050 using a two-sided z-test with continuity correction and allocation ratio of 1:1. The total number of women to be randomised is 2,156, considering a drop-out rate of 15%.

| Target Power | Actual Power | N1 | N2 | N | P1 | P2 | Alpha |
|--------------|--------------|-----|-----|------|------|------|-------|
| 0.80 | 0.80025 | 916 | 916 | 1832 | 0.25 | 0.31 | 0.05 |

Substance Code Clinical Performance and Safety Investigation of **ENDO**metrial Washing
MEdical **DE**vice Forielle
Protocol Number MS 700623_0009

Details when Spending = O'Brien-Fleming, N1=916, N2=916, P1=0,25, P2=0,31, Continuity Correction.

| Look | Time | Lower Boundary | Upper Boundary | Nominal Alpha | Incremental Alpha | Total Alpha | Incremental Power | Total Power |
|------|------|----------------|----------------|---------------|-------------------|-------------|-------------------|-------------|
| 1 | 0.5 | -2.96259 | 2.96259 | 0.003 | 0.003 | 0.003 | 0.16425 | 0.164 |
| 2 | 1 | -1.96857 | 1.96857 | 0.049 | 0.047 | 0.047 | 0.63600 | 0.800 |

The required significance level for stopping the study for clinical performance is 0.003 to first look (50% of patients) and 0.049 at second look (final). The overall power is 80%.

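### The primary model is chosen from trial data by residual sum of squares, which cannot judge a distribution, so the primary test is not fixed in advance

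*Combined protocol and SAP*

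**What the plan says.** Section 8.5.2, repeated in the synopsis, compares mean subject implantation rate between arms with a Gamma or log-normal regression. Treatment is the fixed effect; transfer day, age, follicle count and number of embryos transferred are covariates. No single model is named. The choice is settled by one sentence: "Appropriate distribution will be decided based on good ness of fit (residual sum of squares) value". The scale of the residuals, who decides, when, and whether the interim choice binds the final analysis are not stated.

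The same analysis serves both looks. The study is to be "stopped at significance level of 0.003 in first (50% of subjects) interim analysis and at significance level 0.049 in final analysis".

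Section 8.5.1 adds a general rule: "In the case of normality assumption violations, appropriate non-parametric methods will be used for analysis". It names no method and does not exempt the primary endpoint. It also reserves conclusions about significance for the primary endpoint.

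Details are deferred to a plan that, in the synopsis, "will be prepared separately for interim and final analysis"; section 8.5.1 says the same ("Statistical Analysis Plan (SAP) document developed by separately for interim and final analysis"). Different statisticians, separated by a firewall, run the two analyses. Neither separate plan is among the documents under review.

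**The concern.** A goodness-of-fit rule should ask which distribution describes the data. Residual sum of squares asks only how close the fitted means lie to the observations. It therefore cannot do the job given to it, and the answer it returns depends on an unstated scale.

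The endpoint makes this worse. At most two embryos are transferred, so the rate is essentially 0, 0.5 or 1, and women who are not pregnant are recorded as negative. Neither a Gamma nor a log-normal likelihood exists at zero. Some unstated device, such as an added constant, is needed before either model can use all subjects.

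Such an outcome is also never normal. If the section 8.5.1 fallback reaches the primary endpoint, it is always triggered and conflicts with section 8.5.2.

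At stake is the trial's only confirmatory p-value. The two thresholds are meant to apply to one pre-specified statistic, and the protocol leaves that statistic open.

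**Working it through.** **Inputs from the protocol.** Section 8.1: "Sample sizes of 916 each arm achieve 80% power to detect a difference of 0,06 between the group proportions of 0,25 and 0,31". The test there is two-sided at 0.05 and continuity-corrected, with equal arms, two looks, 15% drop-out and 2,156 randomised. Section 8.6: interim at 1,078 subjects. Section 5.1: at most two embryos.

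**Assumptions not in the protocol.** 70% of women receive two embryos; per-embryo probability is centred on 0.25; correlation within a woman comes from a random effect of SD 0.7; covariate effects are modest; zeros are handled by adding a constant c; Gamma has a log link and Pearson dispersion.

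**1. The plan's own design reproduces.**
- Fixed design without correction: n = [1.960 x sqrt(2 x 0.28 x 0.72) + 0.8416 x sqrt(0.25 x 0.75 + 0.31 x 0.69)]^2 / 0.06^2 = 878 per arm.
- With continuity correction: (878/4) x [1 + sqrt(1 + 4/(878 x 0.06))]^2 = 911.
- The O'Brien-Fleming-type spending function gives bounds 2.9626 and 1.9686, nominal levels 0.00305 and 0.0490, and power 0.8002 at 916 per arm (stated 0.80025).
- 1,832/0.85 = 2,155.3, so 2,156.

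**2. Residual sum of squares does not identify a distribution.** On simulated positive data that were truly log-normal (n = 1,832), the raw-scale sum chose Gamma in 74-78% of trials, while the likelihood chose log-normal in 100%. With each model on its own scale, Gamma was chosen in 100% of trials at a mean of 0.25 and in 0% at a mean of 10, whichever distribution was true.

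The raw-scale preference has a simple cause. A treatment-only Gamma log-link model reproduces the arm means, and arm means minimise the raw sum of squares. With covariates this becomes a tendency.

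**3. A hand check of the own-scale rule.** Take single-embryo transfers and a treatment-only model. The rate plus c takes the values c and 1 + c. The log of a two-valued variable is a straight-line function of it, so the ratio of log-scale to raw-scale residual sums is exactly [ln((1 + c)/c)]^2.

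| c | ratio | smaller sum |
|---|---|---|
| 0.01 | (ln 101)^2 = 21.3 | Gamma |
| 0.1 | (ln 11)^2 = 5.75 | Gamma |
| 0.5 | (ln 3)^2 = 1.21 | Gamma |
| 1 | (ln 2)^2 = 0.48 | log-normal |

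No outcome data enter the ratio; it passes 1 at c = 1/(e - 1) = 0.58. Units matter in the same way. Express the c = 0.01 case in percent (values 1 and 101): the raw sum grows 10,000-fold and the log sum is unchanged. The ratio falls to 21.3/10,000 = 0.002 and the choice reverses.

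**4. Simulated endpoint** (30,000 trials per setting under no effect, looks at 916 and 1,832 subjects, the plan's covariates). About 60% of subjects had a rate of exactly 0. At the final look the raw scale chose Gamma in 100% of trials for every c. The own-scale rule chose Gamma in 100% for c = 0.01, 0.1 and 0.5, and in 0% for c = 1.

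**5. Overall two-sided type I error over both looks (%).** Monte Carlo SE = sqrt(0.05 x 0.95/30,000) = 0.13 points.

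| Analysis | c = 0.01 | 0.1 | 0.5 | 1 |
|---|---|---|---|---|
| Gamma only | 5.25 | 5.15 | 5.03 | 5.01 |
| Log-normal only | 5.17 | 5.13 | 5.13 | 5.04 |
| Rule, own scale | 5.25 | 5.15 | 5.03 | 5.04 |
| Rule, raw scale | 5.25 | 5.15 | 5.03 | 5.01 |
| Smaller p of Gamma and log-normal | 6.90 | 6.42 | 5.76 | 5.47 |
| Smallest p, Wilcoxon added | 7.48 | 7.03 | 6.55 | 6.40 |

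Without any constant, one linear model on the rate (ordinary standard errors) gave 4.97% and Wilcoxon alone 5.05%.

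**The case against.** The strongest reply is that a rule is a rule. Once the scale and the constant are settled, it returned the same model in every simulated trial at the final look. On the raw scale the two looks differed in at most 1 trial in 10,000. That is not p-value shopping, and mechanical use kept the error rate at 5.0-5.3%. This stands, and it limits the point.

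A reader might infer more in four ways, none of which the documents support:

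- **That the rule inflates type I error, or picks the candidate with the worst error rate.** In a further run, Gamma's size left the nominal 4.9% (2.4-7.7%) only with maximum-likelihood dispersion. With Pearson dispersion it was 4.5-5.1%. The protocol names neither estimator.
- **That the two looks will use different models.** Separate plans also fit the firewall and do not show this. What can be said is that nothing prevents it.
- **That section 8.5.1 replaces the primary model with a rank test.** It is a general rule about normality, which a Gamma model does not assume, and it names no method. The defect is that the primary endpoint is not exempted.
- **That an analyst will choose after seeing unblinded results.** The protocol does not say so. It is an inference that the choice needs arm assignment, because treatment is in the model whose residuals are compared.

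The separate plans might settle the matter. But the protocol itself fixes the criterion, so a plan that chose sensibly would have to depart from it.

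**Conclusion.** The point holds as a fault in the selection rule. The criterion cannot judge a distribution. Which model wins depends on the residual scale, the units and the constant used for zeros, and the protocol states neither a scale nor a constant. With an unnamed fallback and no link between the looks, the primary test behind 0.003 and 0.049 is not fixed in advance.

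In size, the error rate is not guaranteed rather than shown to be inflated. It is about 5.0-5.3% if the rule is applied mechanically, and about 5.5-7.5% if an analyst were free to take the most favourable candidate at each look. These figures rest on the assumptions listed above. The hand check in step 3 does not depend on the assumed correlation, event rate or share of two-embryo transfers.

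**What to change.** - Delete the residual-sum-of-squares sentence from section 8.5.2 and from the synopsis.
- Name one primary analysis, the same at both looks and fixed before the interim data cut. It should estimate the difference in mean subject implantation rate, the quantity on which the trial is sized. A linear model on the rate with heteroscedasticity-robust standard errors is one suitable choice: it accepts zeros without an added constant.
- State in section 8.5.1 that the non-parametric fallback does not apply to the primary endpoint.
- Keep any other model as a labelled sensitivity analysis.

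The cost is wording in the protocol and the analysis plans. The sample size stays at 916 per arm and 2,156 in total. Which covariates belong in the model, and how protocol deviations are reviewed, are separate matters that this point does not address.
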